## **Populations for Analyses**

- All Enrolled Subjects: All subjects who sign informed consent form and were confirmed eligible and assigned to a treatment cohort.
- All Treated Subjects: All subjects who receive at least one dose of VK-2019.
- PK Subjects: All subjects who receive at least one dose of study medication and have available VK-2019 plasma concentration data.
- Response Evaluable Subjects: All treated subjects with measurable disease at baseline and one of the following: 1) at least one post-dose tumor assessment, 2) discontinuation prior to the first efficacy assessment due to clinical disease progression or toxicity or 3) death either on treatment or within 28 days of last VK-2019 dose.
- EBV DNA Subjects: All subjects who receive at least one dose of study medication and have available biomarker data.

#### Endpoint Analysis

#### 14.5.1 Analysis of Safety Endpoints

Safety objectives in this study will be assessed using the following endpoints in the All Treated population:

• Incidence of adverse events, SAEs, adverse events meeting protocol-defined DLT criteria, severe adverse events, adverse events leading to study treatment or study discontinuation, and adverse events resulting in death.

- Incidence of clinical laboratory test abnormalities including hematology and serum chemistry abnormalities assessed at protocol designated time points
- Changes in vital signs relative to baseline include blood pressure and heart rate measured at protocol designated time points

## **Adverse Events**

All adverse events will be listed, including the verbatim description and MedDRA preferred term and system organ class (SOC).

Treatment emergent adverse events (TEAEs) are defined as those occurring after the first dose of study treatment.

TEAEs will be summarized by SOC and by preferred term. The incidence of TEAEs will be based on the numbers and percentages of patients with events and number of events. TEAEs will be further summarized by severity (according to NCI CTCAE Version 5.0) and relationship to study treatment.

An overall summary of adverse event incidence will also be presented by dose level to include the number and percentage of patients with at least one: TEAE, treatment related TEAE, Grade 3 to Grade 5 TEAE, death, SAE, treatment related SAE, DLT, TEAE leading to study treatment discontinuation, TEAE leading to dose modifications (e.g. dose reduction) and TEAE leading to study discontinuation.

TEAE data will be presented across all cycles and for each cycle. The denominator for each cycle will be the number of patients available at the start of the cycle who received at least 1 dose of study drug for that cycle.

Individual patient listings will be prepared for all AE data. Listing of the first cycle DLTs for each cohort within each phase will be provided.

## Laboratory Safety Tests

Severity grading, using NCI CTCAE Version 5.0, will be assigned to laboratory safety values where applicable. Laboratory results in reported units and standard international units will be listed, including high and low flags, NCI CTCAE grades where applicable, the corresponding normal range and clinical significance.

Laboratory safety tests summaries will be based on results in SI units. Absolute and change from baseline results will be summarized using descriptive statistics.

Treatment emergent out of range results with the corresponding NCI CTCAE grade, normal ranges, baseline results and clinical significance will be separately listed. Shift tables will be used to show changes from baseline at each timepoint and the worst change in CTCAE grade for each patient.

## Vital Signs and 12-lead ECGs

Absolute and change from baseline vital sign and 12-lead ECG results will be summarized using descriptive statistics. QT analysis intervals will be corrected for heart rate using the Fridericia correction (QTcF). Study conclusions will be based on the most appropriate correction method for the analysis. The effect of VK 2019 concentration on QTcF will be explored after dosing and will be baseline corrected for each patient.

14.5.2 Analysis of Efficacy Endpoints

The Response Evaluable population will be used for all efficacy endpoints with the exception of OS and rate of survival which will use the All Treated population.

The following endpoints will be summarized by dose level and across the Phase 1 and 2a Dose Expansions cohorts for selected doses.

Durable ORR:	The number and percentage of patients who achieve either a complete or partial response that is maintained for at least 6 months.
ORR:	The number and percentage of patients whose best overall response (BOR) is either a complete response (CR) or partial response (PR). To qualify as a responder a patient must have a complete or partial visit response confirmed by a second scan performed at least 4 weeks after the criteria for response are first met.
DOR:	Duration of response (applicable only to patients whose BOR is CR or PR) is defined as the time interval between the date of the earliest qualifying response (complete response or partial response) and the date of disease progression or death for any cause, whichever occurs earlier.
DCR-6 and DCR-12:	The number and percentage of patients who either achieve a best response of either complete response, partial response confirmed by a second scan performed at least 4 weeks later or have stable disease 6 and 12 months after dosing respectively
PFS:	Defined as the interval between the day of the first dose of study treatment to the first documentation of disease progression or death, whichever occurs earlier. Censoring rules will be defined in the Statistical Analysis Plan.
OS:	Defined as the interval between the day of the first dose of study treatment until the date of death because of any cause. Patients who discontinue the study will be censored at the date of their final study visit.
OS-6 and OS-12:	Kaplan-Meier estimates of the proportion of patients alive at 6 and 12 month after the first dose of study treatment respectively using the OS endpoint.

The number and percentage of patients with Durable ORR, ORR, DCR-6 and DCR-12 will be summarized together with exact 95% confidence intervals using a binomial distribution. A Kaplan-Meier method will be used to summarize PFS and OS, from which median values will be presented if reached. Additionally, a Kaplan-Meier method will be used to estimate OS-6 and OS-12.

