## Patient Withdrawal

Patients may withdraw from the trial at any time at their own request, or they may be withdrawn at any time at the discretion of the investigator or sponsor for safety, behavioral, or administrative reasons. Patients that withdraw from treatment should be encouraged to return for the end-of-treatment visit, complete all safety assessments, and enter long-term follow-up. If the patient withdraws from both treatment and follow-up, no further evaluations should be performed, and no additional data should be collected. The Sponsor may retain and continue to use any data collected before such withdrawal of consent.

The primary reason for withdrawal must be recorded in the subject's medical record and in the appropriate eCRF pages. If a subject is withdrawn for more than one reason, each reason should be documented in the source document and the most medically significant reason should be entered on the eCRF. For example, in order to best characterize the safety profile of VK-2019, patients that withdraw consent from treatment due to tolerability issues with VK-2019 should be captured in the eCRFs as having discontinued due to AE or toxicity instead of having withdrawn consent from treatment.

Patients will be discontinued from treatment and begin long-term follow-up in the case of:

- Disease progression or requirement for anticancer therapy not specified in the protocol.
- Inter-current illness, general, or specific changes in the patient's condition where, in the opinion of the Investigator, further treatment is not in the best interest of the patient.
- DLT or unmanageable AE related to therapy.
- Withdraw of consent from treatment.
- Significant protocol violation or non-compliance with protocol.
- Termination of the study by Sponsor. Note: Any patients still receiving investigational product at the time of study termination by the sponsor will be able to continue to receive VK-2019 if they are deriving clinical benefit and after agreement between the Investigator and sponsor. Such patients will continue to be monitored for SAEs as

described in Section 13. Drug Accountability information must still be collected until all patients have completed treatment.

Patients will be withdrawn from study (long-term follow-up) in the case of:

- Withdrawal of consent from follow-up.
- Patient lost to follow-up.
- Death.
- Termination of study by Sponsor.

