#### Interim Analysis

For each dose level expanded, an interim analysis of efficacy will be performed after 16 patients have been dosed. If one or fewer patients have a BOR of CR or PR (not necessarily confirmed 4 weeks later) accrual to this cohort will be stopped.

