7.13 Efficacy

The number and percentage of patients for best overall response (BOR) will be provided. The number and percentage of patients with ORR will also be summarized together with exact 95% confidence intervals (CI) using a binomial distribution for Response Evaluable Population.

The endpoint objective response rate (ORR) is defined as the number and percentage of patients whose best overall response is either a complete response (CR) or partial response (PR). To qualify as a responder, a patient must have a complete or partial visit response confirmed by a second scan performed at least 4 weeks after the criteria for response are first met. A by subject listing will also be provided for Overall Response.

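### PFS and the response rates are analysed only in Response Evaluable patients, which can raise reported response rates, omits some PFS deaths, and does not match the 16 and 25 dosed patients of the Simon rule

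*Protocol*

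**What the plan says.** Protocol 14.5.2 (Analysis of Efficacy Endpoints) sets the rule: "The Response Evaluable population will be used for all efficacy endpoints with the exception of OS and rate of survival". The two exceptions use All Treated. PFS, ORR, durable ORR, DCR-6 and DCR-12, all listed as Phase 2a primary endpoints in Protocol 14.2.1, therefore use Response Evaluable patients.

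Protocol section 14, Populations for Analyses (repeated in SAP 7.3), defines that population as "All treated subjects with measurable disease at baseline and one of the following: 1) at least one post-dose tumor assessment", or "discontinuation prior to the first efficacy assessment due to clinical disease progression or toxicity", or "death either on treatment or within 28 days of last VK-2019 dose".

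SAP 7.13 carries this through for ORR, with "exact 95% confidence intervals (CI) using a binomial distribution for Response Evaluable Population". The SAP contains no analysis of PFS, durable ORR or DCR.

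The decision rule is written on other patients. Protocol section 14, Interim Analysis, places the look "after 16 patients have been dosed". Protocol section 14, Sample Size Determination, and SAP 5 set fixed response counts over 16 and then 25 accrued patients. Neither document says how a dosed but non-evaluable patient counts.

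**The concern.** PFS runs from first dose to progression or death, and ORR is meant to describe patients given the drug at a dose. The analysis population, however, is settled partly by what happens after the first dose. A treated patient who stops before any scan, for example through non-compliance or loss to follow-up, leaves the denominator of every response rate. If that patient dies more than 28 days after the last dose, the death is an OS event and meets the PFS definition, yet it is absent from PFS.

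The measurable-disease condition removes a second group. Inclusion criterion 7 requires measurable disease only in the expansions, while Protocol section 4 counts escalation patients at the same dose toward the 16. An escalation patient without measurable disease can thus be one of the 16 and still be outside the ORR denominator. PFS does not need measurable disease at all.

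At stake are a response rate that reads somewhat too high, PFS and OS reported on different patients, and an expansion decision whose denominator differs from that of the ORR reported beside it.

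**Working it through.** **1. The plan's own figures.** Inputs from Protocol section 14, Sample Size Determination: stop if 1 or fewer responses in 16; reject if 5 or more in 25; response rate 0.10 under the null and 0.30 under the alternative.

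P(reject) = sum over x from 2 to 16 of Bin(x; 16, p) × P(X2 ≥ 5 − x), with X2 binomial on 9 patients.

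- p = 0.10: 0.095 (stated 10%)
- p = 0.30: 0.903 (stated 90%)
- Early stopping at p = 0.10: 0.9^16 + 16 × 0.1 × 0.9^15 = 0.185 + 0.329 = 0.515 (stated 0.51)

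The design reproduces.

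**2. The response rate.** The documents give no non-evaluable count. Assume 0 to 6 of 25 treated patients are excluded, none with a recorded response, and 5 respond. Rate = 5/(25 − k), with exact binomial 95% limits.

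| Excluded k | Denominator | Rate | 95% CI |
|---|---|---|---|
| 0 | 25 | 20.0% | 6.8 to 40.7 |
| 1 | 24 | 20.8% | 7.1 to 42.2 |
| 2 | 23 | 21.7% | 7.5 to 43.7 |
| 3 | 22 | 22.7% | 7.8 to 45.4 |
| 4 | 21 | 23.8% | 8.2 to 47.2 |
| 5 | 20 | 25.0% | 8.7 to 49.1 |
| 6 | 19 | 26.3% | 9.1 to 51.2 |

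The numerator is fixed and the denominator shrinks, so the rate can only rise.

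**3. PFS.** Take a patient with measurable disease who stops in week 3 for a reason other than progression or toxicity, has no scan after dosing, stays in survival follow-up and dies in week 9. Against the definition:

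- Scan after dosing: none. The first scheduled on-treatment scan is at C3D0, after two 28-day cycles (day 56), and the first long-term follow-up scan is 12 weeks after the last dose. The end-of-treatment scan must have been missed.
- Stop for clinical progression or toxicity: no.
- Death on treatment or within 28 days of last dose: no; about 6 weeks (42 days) have passed.

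The patient is outside Response Evaluable. In Protocol 14.5.2 the same death is an OS event in All Treated and fits the PFS definition.

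**4. Decision against report.** A dosed patient without a response adds nothing to the Simon count but remains one of the 16 or 25. In SAP 7.13 the same patient, if non-evaluable, is removed from the ORR denominator.

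**The case against.** The excluded group is narrow. Early stops for clinical progression or toxicity are kept, as are deaths on treatment or within 28 days. Protocol section 6, Patient Withdrawal, says patients who withdraw over tolerability "should be captured in the eCRFs as having discontinued due to AE or toxicity instead of having withdrawn consent from treatment", so they are kept too. The schedules include a tumour assessment at end of treatment, and patients who stop without radiographic progression are scanned every 12 weeks in follow-up; any such scan makes a patient with measurable disease evaluable. All this stands. It limits the number excluded but does not bring it to zero.

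The practical effect is also modest. The SAP serves an abbreviated report, Protocol section 14 plans no confirmatory inference, and in the table above the intervals overlap almost entirely. SAP 7.4 tabulates both populations by cohort and SAP 7.13 lists response by subject, so a reader could rebuild the other rate. That lowers the weight of the point, but the headline figure would still be the selected one.

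Three stronger readings are tempting, and the documents do not support them.

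- A reader might infer that the Simon type I error is inflated. The rule is a response count over dosed patients, enrolment is capped at 25 per dose, and there is no rule for replacing non-evaluable patients. If only 14 and then 22 can respond, the error falls from 0.095 to 0.060.
- A reader might cite lost power: 0.827 at 14 then 22, or 0.858 at 15 then 23, against 0.903. Those figures are right, but they describe equally the case where unassessed patients count as non-responders, which is the remedy here. They are no argument for the change.
- A reader might infer that PFS is shown to be biased upward. Protocol 14.5.2 leaves censoring to the SAP, which gives no PFS rules. An excluded patient who would be censored at day 1 leaves the Kaplan-Meier curve unchanged, and one who withdrew from follow-up as well contributes no later data.

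**Conclusion.** The point holds in limited form. Response Evaluable membership depends partly on events after dosing, and the population drops treated patients without measurable disease as well as those who stop unscanned for other reasons. For response rates the direction is certain, provided the excluded patients have no recorded response. The size is 0.8 to 6.3 percentage points on 20.0% for 1 to 6 excluded of 25; that range is an assumption. For PFS, the omission of some qualifying deaths follows from the text, but upward bias is possible rather than demonstrated. The ORR denominator and the Simon 16 and 25 are never reconciled; this is a problem of reporting and definition, and the design's error rates as stated remain sound. The point should be corrected, but it does not undermine the design.

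**What to change.** - In Protocol 14.5.2, move PFS to All Treated. If PFS is reported, the SAP must also supply the censoring rules that the protocol leaves to it.
- In Protocol 14.5.2, and in SAP 7.13 for ORR, make all treated patients at the dose the denominator for the main ORR, durable ORR and DCR. Count patients without a post-baseline assessment as non-responders (for DCR, as not controlled).
- In Protocol section 14 (Sample Size Determination and Interim Analysis) and SAP 5, state that the 16 and 25 are all patients dosed at that level, including escalation patients with or without measurable disease. Restricting the count to measurable disease would create a new mismatch, because escalation patients count toward the 16 without having to meet that condition.
- Keep Response Evaluable as a supportive analysis.

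The cost is wording in both documents and one further ORR table. PFS, durable ORR and DCR would need new SAP text only if they are to be reported, since the SAP does not now analyse them. Reported rates will be slightly lower.

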## Patient Characteristics and Disposition

All enrolled patients who receive at least one dose of any study medication will be included in the listings and summaries of demographic characteristics, study drug administration and disposition.

Demographic characteristics such as patient age, gender, height, weight, ethnicity, prior therapy, medications, medical history, ECOG performance status and signs and symptoms will be tabulated.

An accounting of the study patients will be tabulated. Patients not meeting the eligibility criteria will be identified. Patients not completing the study will be listed along with the reason for their premature discontinuation. Reasons for premature discontinuation will be summarized.

Study drug administration will be described in terms of the total number of cycles administered, the median (range) of cycles administered, dose intensity, and reasons for deviations from planned therapy.

All medications received during the treatment period will be considered as concomitant medications; patients who received concomitant medications will be listed.

## Pharmacokinetic Analysis

#### 14.7.1 Single- and Multiple-Dose VK-2019 PK Analysis

The PK concentration population is defined as all enrolled patients treated who have at least one concentration evaluation. The PK parameter analysis population is defined as all enrolled patients treated who have at least one of the PK parameters of interest.

Standard plasma pharmacokinetic parameters including the maximum plasma concentration  $(C_{max})$ , time to maximum plasma concentration  $(T_{max})$ , and area under the plasma concentration versus time curve (AUC) for VK-2019 and metabolites will be estimated using non-compartmental analysis. If data permit or if considered appropriate, minimum plasma concentration  $(C_{min})$ , area under the plasma concentration versus time curve to infinity (AUCinf) terminal elimination half-life  $(t_{1/2})$ , oral plasma clearance (CL/F), apparent volume of distribution (Vd/F), accumulation ratio (Rac) will be estimated. If data permit renal clearance (CLR), cumulative amount recovered unchanged in the urine up to 24 hours post-dose (AE24), and cumulative amount recovered unchanged in the urine up to 24 hours post-dose expressed as a fraction of administered dose (AE24%) will be also estimated. In the event of improper urine collection, the cumulative amount recovered unchanged in the urine up to 8 hours post dose (AE8) will be explored. The relative systemic exposure to VK-2019 for the metabolites will also be assessed based on AUC. Descriptive statistics will be provided for these PK parameters in tabular form (N, mean, SD, CV, median, minimum, maximum, geometric mean and its associated CV) by dose, cycle, and day.

For VK-2019 concentrations, individual values and descriptive statistics (N, mean, SD, CV, median, minimum, maximum, geometric mean and its associated CV) will be presented by dose, cycle, day of assessment, and nominal time in tabular form. Individual patient and median profiles of the concentration-time data will be plotted by dose, cycle, and day using nominal times. Median profiles will be presented on both linear-linear and log-linear scales.

Dose normalized VK-2019 AUC and Cmax will be plotted against dose (using a logarithmic scale) by cycle and day. These plots will include individual patient values and the geometric means for each dose. The observed accumulation ratio for VK-2019 and the linearity ratio will be summarized descriptively. The means and 90% confidence intervals (CIs) obtained from the model will be back-transformed to provide means and 90% CI for the accumulation and linearity ratios for each dose.

Confidential

The attainment of steady-state for VK-2019 will be assessed by visual inspection of the pre-dose concentrations on Cycle 1 Day 14 and Cycle 2 Day 0.

## 14.7.2 PK/PD Modeling

Pharmacokinetic/pharmacodynamic modeling may be attempted to investigate any causal relationship between VK-2019 exposure and biomarkers or significant safety endpoints. The results of these analyses, if performed, may be reported separately.

# Pharmacodynamic EBV DNA

Summaries of change from baseline to treatment to post-treatment levels of cell-free plasma EBV DNA will be provided, as appropriate. Individual values and descriptive statistics (N, mean, SD, minimum, maximum, geometric mean and its associated CV) will be presented by dose and cycle in tabular form. The rate of partial response (a reduction by 3xlog10 or more) or complete response (reduction below the LLOD of the assay) will be computed as well.

## Pharmacodynamic EBNA1 inhibition.

Using biopsied material before and after treatment from selected patients, DNA will be isolated and quantitative PCR (qPCR) will be performed. Using validated EBV specific primers, GAPDH control primers, and the Namalwa cell line (which has 2 EBV copies/cell), EBV genome copy number per cell will be assessed. In addition, RNA will be isolated from biopsied material and Nanostring gene expression analysis of viral and cellular genes will be performed. A PanCancer Pathways panel will be used, supplemented with 30 EBV viral genes to assess which pathways are affected by EBNA1 inhibition. These studies will allow us to establish proof-of-mechanism of EBNA1 inhibitors for the treatment of EBV-positive NPC. Individual values and descriptive statistics (N, mean, SD, minimum, maximum, geometric mean and its associated CV) will be presented in tabular form.

